### **Derived covariates**

- Creatinine clearance (CrCL) (mL/min) is estimated depending on age using the following methods:
  1. Original or Bedside Schwartz Equations for pediatric patients:

$$eGFR = k * \frac{\text{height in cm}}{\text{SCR}}$$

- (a) Original Schwartz Equation for participants < 1 year of age:
  - $k = 0.33$  in preemie infants
  - $k = 0.45$  in term infants to 1 year of age
- (b) Bedside Schwartz Equation for participants  $\geq 1$  to  $< 12$  years of age:
  - $k = 0.413$

2. Cockcroft and Gault method for adolescent subjects  $\geq 12$  years of age:

$$CRCL(mL/min) = \frac{[140 - \text{age}(yr)] \cdot \text{Weight}(kg)}{72 \cdot \text{SCR}(mg/dL)} \quad \text{in males}$$

$$CRCL(mL/min) = \frac{0.85 \cdot [140 - \text{age}(yr)] \cdot \text{Weight}(kg)}{72 \cdot \text{SCR}(mg/dL)} \quad \text{in females}$$

Where SCR = serum creatinine concentration.

- Baseline Body Mass Index ( $kg/m^2$ )  
 $BMI = W/H^2$

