##### 4.2.1.7.3 Covariates to be used in the analysis

This updated Population PK model will account for clinically relevant covariates and will include a weight-based allometric scaling of clearance and volume, with fix allometric exponents along with an age-based maturation function for clearance. Covariates in the

latest adult population PK model will be included such as age, body weight, sex, race and eGFR co-morbidity etc. Additional covariates such as body surface area (BSA), body mass index (BMI), albumin, anti-drug antibodies, hepatic function, renal function, SARS-CoV-2 infected or not, viral load, severity of disease, asymptomatic or not, and different co-morbidities may be evaluated as well if deemed appropriate. Co-linearity among covariates will be examined. For pairs with correlation > 80%, a determination will be made as to which variable to retain based on factors such as clinical relevance consistency of variable. The covariates, whenever available, for the population PK analysis will be collected for all subjects who have received AZD7442 and had at least 1 valid serum concentrations. The assessment of each categorical covariate will be done if enough data are available to perform the test, ie if more than 20 subjects or more than 10% of subjects represent this subgroup of covariate. Race will be tested and potentially combined if deemed appropriate, such as combining all Asian populations.

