### **Demographics and baseline clinical chemistry covariates in consideration for investigation**

- Route of Administration (1 = IV Intra Venous; 2 = IM Intra Muscularly)
- Sex (SEX), 1 = males and 0 = females
- Race (RACE), 1 = White; 2 = Black; 3 = Asian; 4 = Other
- Age (AGE), year, weeks
- Body weight (WT), kg
- BMI (kg/m^2)
- Alanine Aminotransferase (ALT)
- Aspartate aminotransferase (AST)
- Estimated Glomerular Filtration Rate (eGFR)
- Serum Creatinine (SCR)
- Total Bilirubin (BIL)
- Serum Albumin
- Co-morbidity information
- Viral Load

Covariates that change over time will be considered in order to obtain values that match the observation time of the dependent variable, such as age and body weight especially in the paediatric patients.

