The latest adult population PK model including covariates will serve as the base model. For additional covariate investigation, the covariate selection will be performed using a forward addition process followed by backward elimination process. The likelihood ratio test will be used to evaluate the significance of incorporating or removing fixed effects into the population model based on significance levels set a priori. For forward addition and backward elimination, significance levels of 0.01 and 0.001 are utilized, respectively. The improvement of the model relative to the base model is compared when each of the covariates is added univariately, and the model with the largest improvement is kept for the next evaluation step, given that there is an overall statistical significance supporting the inclusion of the respective covariate. During the backward elimination process, covariates are removed from the model one at a time if their deletion leads to insignificant model deterioration. The most insignificant covariate is removed first, and the procedure is repeated until no further insignificant covariate relationship is detected.

All continuous covariates are incorporated into the population model using a scaled structure based on either the median value of the covariate in the population or a reference value for the covariate (eg 70 kg for body weight, as was the case in the previous popPK model). This approach ensures that covariate effects are relative to an individual in the middle of the population distribution for that covariate. All categorical covariates are incorporated into the population model using a proportional structure with either the most common level of the covariate being the reference or a level specific to the analysis (eg healthy volunteer versus patient). This approach ensures that categorical covariate effects are relative to a reference group or category. The mathematical structures of the covariate models are shown below:

Continuous	Categorical
$P_{ki} = \theta_k * \left( \frac{X_{ij}}{M(X_j)} \right)^{\theta_j}$	$P_{ki} = \theta_k * (1 + \theta_j)^{X_{ij}}$

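### The renal covariate changes equation at age 12 without a common unit or scale, which could distort the age, weight and sex pattern of paediatric clearance if the covariate is kept on CL

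*SAP*

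**What the plan says.** SAP 4.2.1.7.3, under Derived covariates, states: "Creatinine clearance (CrCL) (mL/min) is estimated depending on age using the following methods". Two methods follow under that one label.

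- **Below 12 years:** k times height divided by serum creatinine (SCR), labelled eGFR, with k = 0.413 from 1 to < 12 years. It has no weight, age or sex term. The text gives no unit for the result or for the creatinine.
- **From 12 years:** "Cockcroft and Gault method for adolescent subjects". This is (140 - age) x weight / (72 x SCR), with SCR in mg/dL and a factor of 0.85 for females. It has no height term.

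The SAP gives no conversion between the two and no sensitivity analysis around age 12.

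On whether a renal term enters the model, SAP 4.2.1.7.3 says that covariates in the "latest adult population PK model will be included such as age, body weight, sex, race and eGFR co-morbidity etc". SAP 4.2.1.7.4 takes the latest adult model, with its covariates, as the base model and describes stepwise selection for additional covariates. Yet the list containing eGFR and serum creatinine is headed "Demographics and baseline clinical chemistry covariates in consideration for investigation", and renal function is also named among covariates that may be evaluated. On functional form: "All continuous covariates are incorporated into the population model using a scaled structure based on either the median value of the covariate" or a reference value, raised to an estimated power.

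**The concern.** A single covariate column should mean the same thing for every participant. Here its inputs change at age 12 from height alone to weight, age and sex. Two children of the same size with the same creatinine, one just under and one just over 12, receive different values for no physiological reason. The size and sign of the difference depend on weight, height and sex.

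The model already carries weight through fixed allometric exponents and age through a maturation function on clearance. Cockcroft-Gault brings weight, age and sex in again, but only from 12 years. A renal term inherited from the adult model would also have its exponent set mainly by adults. SAP Table 5 lists about 50 + 3333 + 750 + 850 = 4983 adults, plus an unstated number from ACTIV-3, against 46 participants in this study's full analysis set. The paediatric data could do little to correct it. At stake is how typical CL is described across paediatric age, weight and sex.

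**Working it through.** The documents state no figure for the difference at age 12, so there is none to reproduce.

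**Inputs from the SAP:** k = 0.413; (140 - age), 72 and 0.85 in Cockcroft-Gault; switch at 12 years.

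**Assumptions, not in the documents:** weights and heights of 12-year-olds from 30 kg/140 cm to 60 kg/155 cm; creatinine in mg/dL in both formulas.

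**Step 1: ratio at age 12.** With weight W (kg) and height H (cm):

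R (boys) = [(140 - 12) x W / (72 x SCR)] / [0.413 x H / SCR] = (128/72)/0.413 x W/H = 4.305 x W/H

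R (girls) = 0.85 x 4.305 x W/H = 3.659 x W/H

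Creatinine cancels. As an example, at 40 kg, 150 cm and an assumed SCR of 0.6 mg/dL:

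- Height formula: 0.413 x 150/0.6 = 103.3.
- Cockcroft-Gault, boy: 128 x 40/(72 x 0.6) = 118.5 (+15%).
- Cockcroft-Gault, girl: 0.85 x 118.5 = 100.7 (-2%).

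**Step 2: range.**

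| Weight/height | W/H | Boys | Girls |
|---|---|---|---|
| 30 kg/140 cm | 0.214 | -8% | -22% |
| 35 kg/145 cm | 0.241 | +4% | -12% |
| 40 kg/150 cm | 0.267 | +15% | -2% |
| 45 kg/150 cm | 0.300 | +29% | +10% |
| 50 kg/155 cm | 0.323 | +39% | +18% |
| 60 kg/155 cm | 0.387 | +67% | +42% |

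The formulas agree only at W/H = 1/4.305 = 0.232 (boys) or 1/3.659 = 0.273 (girls). At 150 cm that is 34.8 kg or 41.0 kg.

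**Step 3: would a unit conversion alone cure it?** Assume that the height formula is indexed to 1.73 m2 (the SAP does not say so), and convert it to absolute mL/min with BSA = sqrt(W x H/3600). For a boy of 42 kg and 150 cm:

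- As written: R = 4.305 x 42/150 = 1.205.
- BSA = sqrt(42 x 150/3600) = 1.32 m2.
- Converted: R = 1.205 x 1.73/1.32 = 1.58.

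Across the assumed range the converted difference is upward for everyone: +48% to +79% in boys and +26% to +52% in girls. It is wider than the unconverted difference in every row of the table except the lightest girls, where -22% becomes +26%. Conversion with both formulas retained does not remove the discontinuity.

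**Step 4: carry-over to CL.** If the covariate acts on CL as a power term with exponent theta, the factor on typical CL is R^theta. The documents give no theta, so 0.1 to 0.5 is assumed. The extremes are R = 0.784 (girl, 30 kg/140 cm) and R = 1.666 (boy, 60 kg/155 cm).

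| theta | R = 0.784 | R = 1.666 |
|---|---|---|
| 0 | 0% | 0% |
| 0.1 | -2% | +5% |
| 0.3 | -7% | +17% |
| 0.5 | -11% | +29% |

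**The case against.** The strongest case against is that the covariate may never matter. Protocol 4.2.1 says AZD7442 is cleared by nonspecific intracellular metabolism, so a null or small renal coefficient is plausible. The SAP does not say that the adult model's eGFR is this derived CrCL, which formula adults had, or which parameter it acts on. If it is an additional covariate, it must pass selection at 0.01 forward and 0.001 backward. Weight exponents are fixed, individual CL carries a random effect informed by the child's own concentrations, and residual plots and stratified visual predictive checks are planned. Non-compartmental CL, where data permit, does not use the covariate. Protocol 9.2 bases the total of 100 on safety; precision of CL supports only the minimum of 24.

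All of this limits the consequence, and it stands. It does not make the definition coherent. If renal function is irrelevant, the term can be dropped; if it is kept, it should mean one thing.

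Two stronger readings are tempting. A reader might infer that every child jumps upward by 20% to 70% on turning 12. At 150 cm that needs a boy of 41.8 to 59.2 kg or a girl of 49.2 to 69.7 kg; lighter children show little change or a fall. Nor is a change within one child established. The SAP says "Covariates that change over time will be considered in order to obtain values that match the observation time of the dependent variable", but its examples are age and body weight, and the chemistry list is headed as baseline. With a baseline value, the discrepancy lies between children on either side of 12. A reader might also infer that the clearance model is certain to contain an artificial step; the conditions above show that it is not.

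**Conclusion.** The point holds in a conditional form and should be corrected. It is certain from the text that one covariate is built from two formulas with different inputs, switched at exactly 12 years and not harmonised. The difference at the boundary is -8% to +67% in boys and -22% to +42% in girls over the assumed weights and heights.

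Whether this reaches paediatric clearance depends on the covariate being retained on CL with a non-zero exponent. The SAP allows that through the adult base model but does not confirm it. With assumed exponents of 0.1 to 0.5, the distortion in typical CL at the extremes runs from a few percent to about 29%. Bias in the reported paediatric CL is therefore possible, not shown. That the two formulas are on different body-size scales also cannot be read from the SAP, which gives the height formula no per-1.73 m2 unit. The argument rests on the formula inputs alone.

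**What to change.** Amend SAP 4.2.1.7.3 as follows.

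1. Use one equation, bedside Schwartz with k = 0.413, for all participants aged 1 to < 18 years. This is the essential step, because converting units while keeping both formulas leaves the break at age 12 and mostly widens it.
2. State that creatinine enters in mg/dL. SAP 4.2.2.2 reports laboratory data in SI units, and only the Cockcroft-Gault expression names a unit.
3. State the adult equation, and put paediatric and adult values on one named scale before they enter the model.
4. Report paediatric CL from a sensitivity run without the renal covariate. This is needed because the change of equation then falls at age 18. For example, if adults use Cockcroft-Gault, an assumed 18-year-old male of 70 kg and 175 cm with SCR 0.9 mg/dL gets 122 x 70/(72 x 0.9) = 132 mL/min. Schwartz gives 0.413 x 175/0.9 = 80.3, or about 86 mL/min after multiplying by 1.845/1.73, on the same BSA assumption as above.

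The cost is a few SAP lines and one extra model run. Height, weight and creatinine are already collected.

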### Subject population

- Healthy volunteers
- Subjects who do not have COVID-19
- Subjects with mild/moderate COVID-19
- Subjects with severe COVID-19

#### 4.2.1.7.4 Structural Population PK Model and Covariate Model Development

Based on prior experience, a 2-compartment model with fixed standard allometric exponents (0.75 for clearances and 1 for volumes) will be evaluated with the inclusion of an age-based maturation function for clearance to represent the paediatric population.

#### Random Effects in the Population PK Model

Inter-individual random effects on the parameters will be introduced and retained if their inclusion do not cause model instability and if their estimates are not close to zero. These will be modeled assuming a log-normal distribution as given by the following expression:

$$\theta_{ki} = \theta_k * e^{\eta_{ki}}$$

where  $\theta_{ki}$  denotes the parameter value for the  $i^{\text{th}}$  subject,  $\theta_k$  denotes the typical parameter value, and  $\eta_{ki}$  denotes the inter-individual random effect for the  $i^{\text{th}}$  subject – assumed to have mean of 0 (zero) and variance  $\omega_k^2$ .

Collectively, the vector of random effects (across the parameters indexed by  $k$ ) has the covariance matrix  $\Omega$ . Covariance matrix structures including diagonal and blocked diagonal structures will be evaluated after the completion of covariate model building.

The residual error structure will be assumed to follow an proportional error model described by the following:

$$Y_{ij} = C_{ij} * (1 + \varepsilon_{1ij})$$

where  $Y_{ij}$  is the  $j^{\text{th}}$  observed concentration for the  $i^{\text{th}}$  subject,  $C_{ij}$  is the corresponding predicted concentration, and  $\varepsilon_{1ij}$  (proportional) is the residual error under the assumption that  $\varepsilon \sim N(0, \sigma^2)$ .

The residual error model will be optimized until no trends are visible in residual plots (in particular, absolute values of IWRES versus IPRED).

Covariates in the latest adult population PK model will be included

The latest adult population PK model including covariates will serve as the base model. For additional covariate investigation, the covariate selection will be performed using a forward addition process followed by backward elimination process. The likelihood ratio test will be used to evaluate the significance of incorporating or removing fixed effects into the population model based on significance levels set a priori. For forward addition and backward elimination, significance levels of 0.01 and 0.001 are utilized, respectively. The improvement of the model relative to the base model is compared when each of the covariates is added univariately, and the model with the largest improvement is kept for the next evaluation step, given that there is an overall statistical significance supporting the inclusion of the respective covariate. During the backward elimination process, covariates are removed from the model one at a time if their deletion leads to insignificant model deterioration. The most insignificant covariate is removed first, and the procedure is repeated until no further insignificant covariate relationship is detected.

All continuous covariates are incorporated into the population model using a scaled structure based on either the median value of the covariate in the population or a reference value for the covariate (eg 70 kg for body weight, as was the case in the previous popPK model). This approach ensures that covariate effects are relative to an individual in the middle of the population distribution for that covariate. All categorical covariates are incorporated into the population model using a proportional structure with either the most common level of the covariate being the reference or a level specific to the analysis (eg healthy volunteer versus patient). This approach ensures that categorical covariate effects are relative to a reference group or category. The mathematical structures of the covariate models are shown below:

Continuous	Categorical
$P_{ki} = \theta_k * \left( \frac{X_{ij}}{M(X_j)} \right)^{\theta_j}$	$P_{ki} = \theta_k * (1 + \theta_j)^{X_{ij}}$

where  $P_{ki}$  is the population estimate of the parameter  $P_k$  for subject  $i$ ,  $X_{ij}$  is the value of continuous covariate  $X_j$  for subject  $i$ , or an indicator variable for subject  $i$  for categorical covariate  $X_j$  with value 1 for the nonreference category and 0 for the reference category,  $M(X_j)$  is the median of covariate  $X_j$  in the analysis dataset,  $\theta_k$  is the typical value of the parameter  $P_k$ , and  $\theta_j$  is a coefficient that reflects the effect of covariate  $X_j$  on the parameter.

To ensure that the model emerging from the covariate testing process did not neglect any important covariate effects, random effects from the final model are plotted versus potential covariates and evaluated for residual trends in parameter covariate relationships.

#### 4.2.1.8 Final Population PK Model

At the end of covariate testing, alternative variance-covariance structures for  $\Omega$  will be evaluated including partial and full block structures. Such a structure is deemed suitable if it provides a statistically significant ( $p < 0.001$ ) improvement in the model OFV and if it improves model stability as measured by the condition number and/or a successful covariance step. The model that results from this step of the model building process is considered the final model.

Further criteria for accepting a model as the final run includes the following:

- The minimization (for gradient methods) is successful.
- There are no estimates close to a boundary.
- Relative standard errors (RSE) of the estimates should be  $< 30\%$  for fixed-effect parameters and  $< 50\%$  for random-effect parameters.
- There are no unacceptable trends in goodness-of-fit plots
- The model allows for the goal of the analysis to be met.
- The parameter shrinkage is acceptable.

Population PK parameter estimates from the final model will be presented, including bodyweight-adjusted clearance for each bodyweight category (adjusted to the mean bodyweight of each weight category). Additionally, the post-hoc individual PK parameter estimates (including AUC0-inf) will be summarized.

#### 4.2.1.9 Evaluation of the Final Population PK Model

Model qualification will be based on criteria including successful numerical convergence, acceptable goodness of fit plots with no indication of bias, adequate precision in parameter estimates evaluating shrinkage in important parameters (CL, V and Ka parameters). In addition, Visual Predictive Checks (VPCs) will be used to evaluate the predictive ability of the final model. Where applicable, VPCs will be performed with prediction correction. Plots of observed data distributions will be compared with simulated distributions to demonstrate the model's ability to adequately predict the data on which the model was based. VPCs will be based on at least 500 simulations and will be stratified by covariates of potential interest. Specifically, VPCs will be stratified by cohort, route of administration and weight category.

#### 4.2.1.10 Subgroup Analyses

No analyses for a specific subgroup are planned.

### 4.2.2 Primary Safety Endpoints

To evaluate the safety and tolerability of AZD7442 after a single IM or IV dose in pediatric participants, the primary safety endpoints will be used: TEAE, SAE, AESI, safety laboratory parameters, electrocardiogram (ECG), vital signs and physical examinations. The analysis of these endpoints will comprise of qualitative or quantitative summary statistics.

All summaries of primary safety endpoints will be based on the SES, listings will be created for the SAF.

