8.5.1 Total Blood Volume

Blood volume estimates are provided in **Table 16**. For participants other than neonates, the total estimated blood volume to be collected during the study is approximately 73 mL per participant. For neonates, only safety and PK samples will be collected and the total estimated blood volume to be collected during the study is approximately 22 mL per participant. The total volume can be adjusted by age and the body weight of the participant per local ethics requirements. Where necessary, the visit windows in the SoA can be used to collect samples across a number of days. When sample collection occurs over ≥ 2 days for a given study visit, participants are required to visit the site at least once per study visit. If practical, additional sample collection can take place at home visits as long as the samples are obtained per protocol by qualified personnel. If it is not possible to obtain sufficient blood from a participant at a given study visit, the order of the samples will be prioritized according to the key requirements of the study and the following hierarchy will be applied: safety (ie, serum chemistry, hematology, coagulation), PK, SARS-CoV-2 neutralizing antibodies, and ADA (see Laboratory Manual). For participants receiving IV infusions of AZD7442, blood samples are to be collected from the opposite side of the body to the IV infusion at Visit 1.

Table 16 Blood Volume Estimates

Visit (study day \pm visit window)	Estimated blood volume for neonates ^a	Estimate blood volume for all other participants ^b
Screening Visit (Day -7 to Day 0)	3.7 mL	6.3 mL
Visit 1 (Day 1 \pm 0)	1.2 mL (IV only)	6.0 to 8.5 mL ^{c, d}
Visit 2 (Day 4 to 15 \pm 2)	1.2 mL	2.5 mL
Visit 3 (Day 31 + 5)	4.9 mL ^e	14.8 mL
Visit 4 (Day 92 \pm 5)	2.6 mL ^e	10.3 to 12.8 mL ^d
Visit 5 (Day 183 \pm 10)	3.5 mL ^e	13.0 mL
Visit 6 (Day 366 \pm 15)	4.9 mL ^e	14.8 mL
Total from screening to Day 366	20.8 to 22.0 mL	67.7 to 72.7 mL

^a For neonates, only safety and PK samples will be collected.

^b For participants other than neonates, the following hierarchy will apply if it is not possible to obtain blood for all samples: (1) safety, (2) pharmacokinetics, (3) SARS-CoV-2 neutralizing antibodies, and (4) anti-drug antibodies.

^c At Visit 1, participants receiving AZD7442 IV will have an extra 2.5mL blood sample taken for post-dose PK sampling.

^d At Visit 4, participants in Cohort 1 will also have an additional 2.5mL taken for SARS-CoV-2 serology.

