**Table 1: Analysis sets**

Population/Analysis Set	Description
Screened Population Set (SPS)	All participants who signed the ICF. Unless otherwise stated, this set will be used for the presentation of disposition data.
Full Analysis Set (FAS)	All participants who received the IMP, irrespective of their protocol adherence and continued participation in the study. Participants who withdraw consent or assent to participate in the study will be included up to the date of their study termination.
Modified Full Analysis Set (mFAS)	All participants who are in the FAS, excluding participants who were assigned to Cohort 1 by rapid COVID-19 test, but have a positive confirmatory test.
Safety Analysis Set (SAF)	All participants who have received IMP.
PK Analysis Set (PKS)	All participants who received AZD7442 and from whom PK blood samples are assumed not to be affected by factors such as protocol violations, and who had at least one quantifiable serum PK observation post-dose, will be included in the PK analysis dataset.
AZD1061 ADA Evaluable Analysis Set (ADS1)	A participant is AZD1061 ADA evaluable if in the SAF and having a non-missing baseline AZD1061 ADA result and at least one non-missing post-baseline AZD1061 ADA result.
AZD8895 ADA Evaluable Analysis Set (ADS2)	A participant is AZD8895 ADA evaluable if in the SAF and having a non-missing baseline AZD8895 ADA result and at least one non-missing post-baseline AZD8895 ADA result.
AZD7442 ADA Evaluable Analysis Set (ADS3)	All participants who are AZD8895 ADA evaluable and/or AZD1061 ADA evaluable.
SARS-CoV-2 nAb Evaluable Analysis Set (SES)	All participants in the Safety Analysis Set from whom blood samples were assumed not to be affected by factors such as protocol violations, and who had at least one quantifiable serum titer observation post dose.

Generally, all listings will be prepared based on the SAF unless otherwise stated.  
Disposition data will be listed for the SPS.

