#### **4.1.3 Protocol Deviations**

##### **4.1.3.1 Definitions and Derivations**

Important deviations from the protocol (IPDs) may lead to the exclusion of participants or data from the PKS or SES. Deviations will be assessed and classified during the study and finalized before database lock. IPDs include those deviations from the protocol that are likely to have an impact on the perceived safety of study treatments or outcome assessment.

IPDs will include the following at a minimum:

- Violation of key inclusion and/or exclusion criteria.
- Administration of prohibited concomitant medications that are expected to influence the outcome of this study.
- Deviations from planned dose or administration procedure of the IMP.
- Relevant time window deviations expected to influence key safety and/or PK assessments.

All important protocol deviations will be listed. A qualitative summary table will be provided.

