### 4.2 Endpoint Analyses

This section covers details related to the endpoint analyses such as primary, secondary, other endpoints. Sensitivity analyses are done by repeating the endpoint analyses using a sensitivity analysis set if indicated in [Table 2](#). The analysis sets shown are applicable to the tables of the endpoints. Listings may utilize other sets. All endpoint analyses will be descriptive qualitative or quantitative summaries.

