**Table 2: Analysis Endpoints**

Objectives	Endpoints	Analysis Set
Primary		
To evaluate the serum concentrations of AZD7442 after a single IM or IV dose in pediatric participants	Serum concentrations of AZD7442 at specified time points during the one-year study period when administered as a single IM or IV dose  Serum PK parameters (if data permits): Cmax, tmax, t1/2, AUC0-last , AUC0-inf , tlast, %AUCext, and: 

• for IM: CL/F, and Vz/F

• for IV: CL, and Vss

 Model-derived predicted serum AZD7442 concentrations, Cmax and AUC0-inf	PKS
To evaluate the safety and tolerability of AZD7442 after a single IM or IV dose in pediatric participants	TEAEs, SAEs, and AESIs (including anaphylaxis, injection/infusion site reactions, MIS-C).  Safety laboratory parameters (hematology, clinical chemistry, coagulation, and urinalysis); 12 lead safety ECG; vital signs (BP, pulse rate, tympanic membrane temperature, and respiratory rate), and physical examination.	SAF
Secondary – All Cohorts		

Objectives	Endpoints	Analysis Set
To evaluate the PD of AZD7442 after a single IM or IV dose	Titer of SARS-CoV-2 neutralizing antibodies	SES
To evaluate the immunogenicity profile of AZD7442	Incidence of ADA and nAb to AZD7442 in serum	ADS1/2/3
Secondary – Cohort 1 (Prophylaxis)		
To evaluate the incidence of SARS-CoV-2 infections with or without COVID-19 symptoms after a single IM or IV dose of AZD7442 in pediatric participants	Incidence of SARS-CoV-2 infections with and without COVID-19 symptoms	SAF, mFAS
Secondary – Cohort 2 and Cohort 3 (Treatment)		
To quantify SARS-CoV-2 viral loads after a single IM or IV dose of AZD7442 in pediatric participants	Change from baseline to Day 8 in viral load as measured by qRT-PCR.	SAF
To evaluate the proportion of participants with progression of COVID-19 after a single IM or IV dose of AZD7442 in pediatric participants	Proportion of participants with progression of COVID-19 through Day 29	SAF
To evaluate COVID-19 related death through 90 days after a single IM or IV dose of AZD7442 in pediatric participants	The incidence of COVID-19-related death occurring after dosing with IMP up to study day 90	SAF
Secondary – Cohort 3 (Severe COVID-19)		

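### SAP 4.2.2 puts every primary safety summary on the neutralising-antibody set (SES), while SAP Table 2 assigns the same endpoints to the Safety Analysis Set (SAF)

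*SAP*

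**What the plan says.** SAP Section 4.2.2 covers TEAEs, SAEs, AESIs, safety laboratory parameters, ECG, vital signs and physical examination. Its instruction on analysis sets is: "All summaries of primary safety endpoints will be based on the SES, listings will be created for the SAF".

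SAP Table 1 defines the two sets:

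- SAF: "All participants who have received IMP".
- SES: members of the SAF whose blood samples are taken to be unaffected by factors such as protocol violations, and "who had at least one quantifiable serum titer observation post dose". Protocol Table 17 defines the same set.

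SAP Section 4.1.3.1 adds: "Important deviations from the protocol (IPDs) may lead to the exclusion of participants or data from the PKS or SES".

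SAP Table 2 gives the SAF as the analysis set for the row that begins "TEAEs, SAEs, and AESIs (including anaphylaxis, injection/infusion site reactions, MIS-C" and for the laboratory, ECG, vital-sign and physical-examination endpoints. SAP Section 4.2 says of that table: "The analysis sets shown are applicable to the tables of the endpoints".

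On sampling, Protocol Section 8.5.1 says: "For neonates, only safety and PK samples will be collected".

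**The concern.** Safety is a co-primary objective, and its denominator should be everyone who was dosed. Section 4.2.2 replaces that with a pharmacodynamic set whose membership depends on what happens after dosing: staying in the study long enough, giving enough blood for a titre, and having a quantifiable result. Those conditions are related to age, survival, retention and the conduct of dosing, so the exclusion may be informative.

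Two groups matter most. Neonates, whom Protocol 4.2.2 stratifies separately because of their susceptibility, would be missing from every primary safety table. Participants with the earliest and most serious events could be missing from the adverse event tables. The percentages, exact confidence intervals and exposure-adjusted rates would then describe children who gave a usable titre, not children who received AZD7442.

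**Working it through.** The plan states no size for the SES, so there is no figure to reproduce. The check is on set membership, followed by an illustration of scale.

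**1. The two instructions side by side**

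| Place in SAP | Set for primary safety tables |
|---|---|
| Section 4.2.2 | SES (SAF for listings only) |
| Table 2, read with Section 4.2 | SAF |

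Both are current text, neither is changed by the amendment history, and no rule says which prevails. Section 4.2.2 names both sets and gives each a different role, so a programmer following it would use the SES.

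**2. Neonates cannot enter the SES**

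The neonatal schedule (Protocol Table 2) has a serum PK row and no neutralising-antibody row. The volumes in Protocol Table 16 confirm this:

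- PK sample: 1.2 mL (Visit 2).
- Chemistry and haematology: Visit 5 total minus PK = 3.5 − 1.2 = 2.3 mL.
- Coagulation: Visit 4 total minus PK = 2.6 − 1.2 = 1.4 mL.
- Safety samples together: 2.3 + 1.4 = 3.7 mL, which equals the screening volume.
- Visits 3 and 6: 3.7 + 1.2 = 4.9 mL, as tabulated.

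No volume is left for a titre. Protocol Table 5 planned at least 2 + 2 = 4 neonates out of 100.

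**3. Who else can fall outside the SES**

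- Protocol Table 3 schedules neutralising-antibody samples pre-dose and at Days 31, 92, 183 and 366, plus the early discontinuation visit. Protocol 7.2 asks for that visit only where possible. A child who dies or is lost before Day 31 without it has no post-dose titre.
- If too little blood can be drawn, neutralising antibodies rank third, after safety and PK (Protocol 8.5.1).
- Important deviations may remove participants or data from the SES, and SAP 4.1.3.1 counts departures from the planned dose or administration procedure among them. A safety table needs those participants.
- At an interim analysis, dosed participants who have not reached Day 31 would be outside the SES, although SAP Section 5 calls for all available data.

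**4. Scale**

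SAP Section 2 gives 46 participants in the full analysis set, which has the same dosing condition as the SAF. SAP 4.2.2.1 specifies exact Clopper-Pearson 95% intervals. For zero events the upper limit is 1 − 0.025^(1/n). The number excluded is an assumption, shown over a range:

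| Assumed excluded | n | Upper limit, 0 events |
|---|---|---|
| 0 (SAF) | 46 | 7.7% |
| 2 | 44 | 8.0% |
| 4 | 42 | 8.4% |
| 7 | 39 | 9.0% |
| 10 | 36 | 9.7% |

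If one SAE occurs in an excluded child, the SAF table shows 1/46 = 2.2% (exact 95% CI 0.1% to 11.5%). With 4 excluded, the SES table shows 0/42.

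**The case against.** The strongest reply is that SES is a slip for SAF. Table 2 already names the SAF, Section 4.2 says Table 2 governs the tables, and demographics (4.1.4) and injection/infusion site inspection (4.2.8.2) are on the SAF. Listings stay on the SAF too, so no individual event disappears from the report. A slip is indeed the likely explanation. It does not settle which instruction is followed, and listings do not supply incidences or confidence intervals.

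The size of the effect is also open to challenge, and these limits stand:

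- The figure of 4 neonates is a minimum from the 100-participant design. The number among the 46 is not given and could be zero.
- The limits above are pooled, whereas SAP 4.2.2.1 presents adverse events by cohort and route. That split is not given, so the effect on the reported tables cannot be computed.
- Early loss of non-neonates bears mainly on adverse events and early vital signs. Their scheduled post-dose laboratory tests start at Day 31 and the post-dose ECG is at Day 366, apart from the discontinuation visit, so early leavers contribute little of that data under either set.
- The documents give no missingness by age or size. That the smallest children are likeliest to miss the titre is an inference from the sampling hierarchy, and sampling may be spread over several days.

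None of this affects the exclusion of neonates, which applies to the adverse event, laboratory, ECG and vital-sign tables alike.

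**Conclusion.** The concern holds. Section 4.2.2 names the wrong set and conflicts with Table 2. Followed literally, it removes every neonate and anyone else without a usable post-dose titre from all primary safety summaries. The loss of precision is modest: with 2 to 10 of 46 assumed excluded, the zero-event upper limit goes from 7.7% to between 8.0% and 9.7%. The more serious risk is that events in excluded children vanish from the tables. The actual loss depends on how many of the 46 are outside the SES, which the documents do not report, and on 4.2.2 being programmed as written. This must be corrected because it sets the denominator of every co-primary safety table.

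**What to change.** In SAP Section 4.2.2, replace SES with SAF so that primary safety summaries and listings both use all dosed participants, in agreement with SAP Table 2. Keep the SES for the neutralising-antibody titre summaries in Section 4.2.3.1. Make the change before database lock, and check that the table shells and programs for adverse events, laboratory data, vital signs and ECG use the SAF. The cost is a one-word correction, with no new data and no operational change.
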